8.1. Adverse Events Analyses

Adverse events analyses including the analysis of adverse events (AEs), Serious (SAEs) and other significant AEs will be based on GSK Core Data Standards. The details of the planned displays are provided in [Appendix 10: List of Data Displays](#).

All AEs will be classified using the standard GSK Medical Dictionary for Regulatory Activities (MedDRA) dictionary, and grouped by SOC and PT, unless otherwise stated. The investigator will evaluate all AEs with respect to seriousness, severity, and causality.

AEs analyses will be by treatment group (and total for GTC1, GTC2, GTC3 and Overall) and study phases (i.e., TC1, TC1 <= 84 days, GTC1, GTC2, GTC3 and Overall, see section [11.4](#)). Note that Overall includes all AEs after GSK1358820 treatment.

The number and percentage of subjects experiencing an AE and the total number of AEs (the number of subjects with any AEs) will be summarized for each of the following AE categories by treatment group (and total for GTC1, GTC2, GTC3 and Overall):

- All AEs (by SOC and PT; by SOC and PT and maximum severity)
- Serious AEs (by SOC and PT)
- Treatment related AEs (by SOC and PT; by SOC and PT and maximum severity)

- Study drug related AEs (by SOC and PT; by SOC and PT and maximum severity)
- Injection related AEs (by SOC and PT; by SOC and PT and maximum severity)
- Serious treatment related AEs (by PT, for PLS)
- Non-serious treatment related AEs (by PT, for PLS)

The tabular summary for each category of AE listed above will include the number of subjects who reported at least one event, and percentage of subjects who reported at least one AE (incidence) by treatment group (and total for GTC1, GTC2, GTC3 and Overall) for each SOC (where applicable), each PT, and overall. By default, adverse events will be sorted by MedDRA SOCs, in descending order from the SOC with the highest total incidence (i.e., summed across all treatment groups) for any adverse event within the class, to the SOC with the lowest total incidence. If the total incidence for any two or more adverse events is equal, the events will be presented in alphabetical order. Only SOCs with observed AE PTs will be presented. Repeat sort order for MedDRA PTs within each SOC.

Common AEs will not be summarized, except for the analysis of requirement by FDAAA and EudraCT. Because the number of subjects is small (target is N=30, so expected number of subjects is about 15/treatment group), if only 1 subject had a given AE, percentage of subjects who had that AE is over 5%. Therefore, summary of common AE is meaningless in this study. As for requirement by FDAAA and EudraCT, the number and percentage of subjects and the number of events will be summarized for common ($\geq 5\%$) non-serious AEs by SOC and PT in TC1, GTC1, GTC2 and GTC3.

Any subgroup analysis for AEs will not be produced.

As for AEs by SOC and PT and severity, the number and percentage of subjects will be summarized as mild, moderate and severe on the maximum severity observed within each PT for a given subject.

Listing will be produced for each of the following AE categories:

- All AEs
- Serious AEs
- AEs resulting in withdrawal from study

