#### 4.1. Overall Design

#### 4.2. Treatment Arms and Duration

This study consists of a Screening phase (within the 28 day-period before first treatment), a Treatment phase 1 (double-blind treatment phase: 12 to 48 week period after first treatment), and a Treatment phase 2 (open-label treatment phase: 12 to 36 week period after first treatment). The duration of overall treatment phase is 48 weeks

Following the Screening phase, patients meeting the eligibility criteria will be randomly assigned by the registration center to one of the 2 treatment arms (either 200 U GSK1358820 or placebo) in a ratio of 1:1. Subsequently, in Treatment phase 1, patients will receive single treatment with the allocated study drug (30 injections each of 1.0 mL) which will be injected into the detrusor of bladder. At the randomization, patients will be stratified according to NDO etiology (spinal cord injury [SCI] with neurological injury level C5 to C8, SCI with neurological injury level T1 or below, or multiple sclerosis[MS]).

Subjects who meet the criteria for re-treatment (referred Re-treatment criteria) between 12 to 36 weeks after 1st treatment can enter to Treatment phase 2 to receive re-treatment (GSK1358820 200 U). Patients are permitted to receive re-treatment up to 36 weeks after 1st treatment and at most 2 times (Note: a minimum of 12 weeks need to be elapsed since the previous study treatment). Subjects who did not receive re-treatment will remain in the Treatment phase 1 and continue to visit at the scheduled study visit. Observation period will be the 48 week period after 1st treatment and patients who complete the evaluation at 48 weeks after 1st treatment are regarded as the patients who complete the study, regardless of whether the subject was re-treated or not.

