- (b) Patient can request 2nd re-treatment at any time via telephone since week 12 after re-treatment. If the patient requests re-treatment via telephone, a qualification for re-treatment visit should be conducted within approximately 1-2 weeks of the patient request.
- (c) Bladder diary must have been completed for any 3 consecutive days in the week prior to the visit. The volume voided is recorded by subjects for one 24-hour period during the 3 day diary collection period.
- (d) Measured only body weight
- (e) Performed prior to treatment
- (f) These examination can be completed at the Qualification for re-treatment visit or at any time within 21 days prior to re-treatment
- (g) Urine culture and sensitivity is performed by the central laboratory when dipstick results are positive for nitrites or leukocyte esterase
- (h) For patients with doubtful reaction in urinary pregnancy test, the investigator (or subinvestigator) may conduct serum pregnancy test.
- (i) For patients without a UTI as determined from the urinalysis or urine culture and/or investigator opinion, prophylactic antibiotic are to be administered 1 to 3 days before study treatment, on the day of treatment, and 1 to 3 days after treatment. For patients with a UTI as determined from the urinalysis or urine culture and/or investigator opinion, an antibiotic to which the identified organism is sensitive is to be administered at least 5 days prior to study treatment and continued for at least 3 days following the procedure.
- (j) Patients who are not retreated will continue to visit at the scheduled study visit.
- (k) Re-treatment must be occurred after a minimum of 12 weeks (84 days) have elapsed since the previous treatment. Re-treatment should not have occurred later than 36 weeks after 1st treatment
- (l) If qualification for re-treatment criteria was met, the patient will undergo the exams specified in the column marked "If qualification for re-treatment criteria was met"

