11.4.1.2. Study Phases for AE Data

Treatment State	Definition
Pre-Treatment	AE Start Date < Study Treatment Start Date
On-Treatment	If AE onset date is on or after treatment start date & on or before treatment stop date. Study Treatment Start Date \leq AE Start Date \leq Study Treatment Stop Date
Onset Time Since 1st Dose (Days)	If Treatment Start Date > AE Onset Date = AE Onset Date - Treatment Start Date If Treatment Start Date \leq AE Onset Date = AE Onset Date - Treatment Start Date +1 Missing otherwise.
Duration (Days)	AE Resolution Date – AE Onset Date + 1
Treatment Cycle 1 (TC1) \leq 84 days from 1st treatment	1st treatment Date \leq AE Start Date \leq 1st treatment Date +83
Treatment Cycle 1 (TC1)	1st treatment Date \leq AE Start Date (if the subject completes / withdraws without 2nd treatment) \leq Study Exit/Withdraw Date or (if the subject take 2nd treatment) < 2nd treatment Date

Treatment State	Definition
GSK1358820 Treatment Cycle 1 (GTC1)	For subjects who received GSK1358820 as 1st treatment: 1st treatment Date \leq AE Start Date (if the subject completes / withdraws without 2nd treatment) \leq Study Exit/Withdraw Date or (if the subject take 2nd treatment) $<$ 2nd treatment Date For subjects who received placebo as 1st treatment: 2nd treatment Date / Time \leq AE Start Date / Time (if the subject completes / withdraws without 3rd treatment) \leq Study Exit/Withdraw Date or (if the subject take 3rd treatment) $<$ 3rd treatment Date
GSK1358820 Treatment Cycle 2 (GTC2)	For subjects who received GSK1358820 as 1st treatment: 2nd treatment Date / Time \leq AE Start Date / Time (if the subject completes / withdraws without 3rd treatment) \leq Study Exit/Withdraw Date or (if the subject take 3rd treatment) $<$ 3rd treatment Date For subjects who received placebo as 1st treatment: 3rd treatment Date / Time \leq AE Start Date / Time \leq Study Exit/Withdraw Date
GSK1358820 Treatment Cycle 3 (GTC3)	For subjects who received GSK1358820 as 1st treatment: 3rd treatment Date / Time \leq AE Start Date / Time \leq Study Exit/Withdraw Date For subjects who received placebo as 1st treatment: Not applicable because 3 rd treatment of GSK1358820 is not allowed for subjects who received placebo as 1st treatment
Overall	For subjects who received GSK1358820 as 1st treatment 1st treatment Date \leq AE Start Date \leq Study Exit/Withdraw Date For subjects who received placebo as 1st treatment 2nd treatment Date \leq AE Start Date \leq Study Exit/Withdraw Date

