11.10.8. Safety Tables

Safety : Tables						
No.	Population	IDSL / TST ID / Example Shell	Title	Programming Notes	Report at Interim	Report at Final
Adverse Events (AEs)						
3.1.	SPDB	AE1	Summary of All Adverse Events TC1 <= 84 days from the first treatment	ICH E3	Y	
3.2.	SPDB	AE1	Summary of All Treatment-Related Adverse Events TC1 <= 84 days from the first treatment	GSK CTR	Y	
3.3.	SPDB	AE1	Summary of All Study Drug-Related Adverse Events TC1 <= 84 days from the first treatment	GSK CTR	Y	
3.4.	SPDB	AE1	Summary of All Injection Procedure-Related Adverse Events TC1 <= 84 days from the first treatment	GSK CTR	Y	
3.5.	SPDB	AE5A	Summary of All Adverse Events by maximum severity: TC1 <= 84 days from the first treatment	ICH E3	Y	
3.6.	SPDB	AE5A	Summary of All Treatment-Related Adverse Events by maximum severity: TC1 <= 84 days from the first treatment	GSK CTR	Y	
3.7.	SPDB	AE5A	Summary of All Study Drug-Related Adverse Events by maximum severity: TC1 <= 84 days from the first treatment	GSK CTR	Y	
3.8.	SPDB	AE5A	Summary of All Injection Procedure-Related Adverse Events by maximum severity: TC1 <= 84 days from the first treatment	GSK CTR	Y	
3.9.	SPDB	AE1	Summary of All Adverse Events TC1	ICH E3	Y	Y

CONFIDENTIAL

204948

Safety : Tables						
No.	Population	IDSL / TST ID / Example Shell	Title	Programming Notes	Report at Interim	Report at Final
3.10.	SPDB	AE1	Summary of All Treatment-Related Adverse Events TC1	GSK CTR	Y	Y
3.11.	SPDB	AE1	Summary of All Study Drug-Related Adverse Events TC1	GSK CTR	Y	Y
3.12.	SPDB	AE1	Summary of All Injection Procedure-Related Adverse Events TC1	GSK CTR	Y	Y
3.13.	SPDB	AE5A	Summary of All Adverse Events by maximum severity: TC1	ICH E3	Y	Y
3.14.	SPDB	AE5A	Summary of All Treatment-Related Adverse Events by maximum severity: TC1	GSK CTR	Y	Y
3.15.	SPDB	AE5A	Summary of All Study Drug-Related Adverse Events by maximum severity: TC1	GSK CTR	Y	Y
3.16.	SPDB	AE5A	Summary of All Injection Procedure-Related Adverse Events by maximum severity: TC1	GSK CTR	Y	Y
3.17.	SPDB	AE15	Summary of Subjects and Number of Occurrences of Common Non-Serious Adverse Events TC1	FDAAA, EudraCT	Y	Y
3.18.	SP1	AE1	Summary of All Adverse Events: GTC1	ICH E3		Y
3.19.	SP1	AE1	Summary of All Treatment-Related Adverse Events: GTC1	GSK CTR		Y
3.20.	SP1	AE1	Summary of All Study Drug-Related Adverse Events: GTC1	GSK CTR		Y
3.21.	SP1	AE1	Summary of All Injection Procedure-Related Adverse Events: GTC1	GSK CTR		Y

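### Full-cycle TC1 adverse-event percentages compare arms whose follow-up can differ with efficacy, and the SAP does not name the equal-follow-up (≤84-day) window as the between-arm comparison or carry it into the final and disclosure tables

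*SAP*

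**What the plan says.** **Length of TC1.** Protocol 4.2 describes the "double-blind treatment phase: 12 to 48 week period after first treatment" and adds: "Subjects who did not receive re-treatment will remain in the Treatment phase 1 and continue to visit at the scheduled study visit". For adverse events (AEs), SAP 11.4.1.2 starts TC1 at the first injection. It stops at exit or withdrawal or, "if the subject take 2nd treatment) < 2nd treatment Date", which means the day before re-injection. Under Protocol 5.3, re-treatment needs a patient request and at least 4 incontinence episodes on the 3-day diary, among other criteria. SAP 7.2.1 analyses time to that request, and to qualification, as duration of treatment effect.

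**Summary measure.** SAP 8.1 sets the layout: "AEs analyses will be by treatment group (and total for GTC1, GTC2, GTC3 and Overall) and study phases". It tabulates the "percentage of subjects who reported at least one AE (incidence) by treatment group", with event counts. No person-time rate or time-to-first-event analysis of AEs is planned.

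**Equal-follow-up window.** Protocol 9.4.2 plans a summary for the first 12 weeks, and SAP 11.4.1.2 defines it as the first treatment date to +83 days. Protocol Table 2, footnote (k), states: "Re-treatment must be occurred after a minimum of 12 weeks (84 days) have elapsed since the previous treatment".

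**Which tables run when (SAP 11.10.8).**
- The ≤84-day tables are 3.1-3.8 (the first is "Summary of All Adverse Events TC1 <= 84 days from the first treatment"), 3.53 (serious AEs) and 3.54 (special interest). They are marked for the interim only, and SAP 11.10.1 starts the final safety numbering at 13.9.
- The full-TC1 tables 3.9-3.17 and 3.55-3.57 are marked for interim and final.
- The FDAAA/EudraCT tables for the double-blind phase use full TC1: 3.17 ("Summary of Subjects and Number of Occurrences of Common Non-Serious Adverse Events TC1") and 3.56. So do the plain-language tables 3.69 and 3.74, which run at final only.

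**The concern.** Safety compared with placebo is a stated objective. In the full-TC1 tables, the time during which a subject can contribute an event is set by how long the treatment works. If the drug works as expected, placebo subjects tend to request re-treatment sooner and leave TC1, while active subjects stay in it longer. A crude percentage then mixes risk per unit of time with length of observation. Two arms with the same weekly risk could show different percentages, with the higher one on active.

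The plan has a window without this problem, but no sentence says that it is the one to use for comparing arms. A reader of the final tables, the FDAAA/EudraCT postings or the plain-language summary would see only the full-TC1 contrast.

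**Working it through.** **Inputs from the documents.** TC1 lasts 12 to 48 weeks (Protocol 4.2), a range of 48/12 = 4-fold between subjects. The short window runs from day 0 to day +83, which is 84 days, and no re-treatment is allowed before 84 days have elapsed. Follow-up in it is therefore equal by design, withdrawals aside. SAP 8.1 notes that with about 15 per arm a single subject exceeds 5%; 1/15 = 6.7% confirms this.

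**Inputs that must be assumed.** The documents give neither re-treatment times by arm nor AE hazards after week 12. I take the same hazard in both arms, a 12-week risk p = 20%, and a hazard after week 12 equal to f times the earlier hazard.

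**Formula.** h = −ln(1 − p)/12 = −ln(0.80)/12 = 0.0186 per week. For T ≥ 12 weeks, cumulative incidence is R(T) = 1 − exp{−h[12 + f(T − 12)]}. The artefact is R(T active) − R(T placebo). Differences are taken before rounding.

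| f | R(16) | R(36) | 36 v 16 weeks | 24 v 12 weeks | 48 v 12 weeks |
|---|---|---|---|---|---|
| 0 | 20.0% | 20.0% | 0 | 0 | 0 |
| 0.25 | 21.5% | 28.4% | 7.0 | 4.3 | 12.3 |
| 0.5 | 22.9% | 36.0% | 13.1 | 8.4 | 22.8 |
| 1 | 25.7% | 48.8% | 23.1 | 16.0 | 39.0 |

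For example, with f = 1, R(36) = 1 − 0.8³ = 48.8% and R(16) = 1 − 0.8^(16/12) = 25.7%. The last column is the extreme case. With equal follow-up in both arms every difference is 0. Since 7.0/6.7 ≈ 1 and 23.1/6.7 ≈ 3.5, the 36 v 16 range corresponds to about 1 to 3.5 subjects in an arm of 15.

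**Other base risks, 36 v 16 weeks, f = 0.25 to 1.** With p = 10%, the artefact is 3.8 to 14.0 points. With p = 35.7%, it is 10.4 to 28.9 points. The latter is the placebo urinary tract infection (UTI) figure in Protocol 4.6.1, treated as a 12-week risk; the protocol does not give its period.

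**Where a real difference exists.** Take the same section's UTI figures, 49.2% (200 U) and 35.7% (placebo), as 12-week risks. The difference is 49.2 − 35.7 = 13.5 points at equal 12-week follow-up. At 36 v 16 weeks it becomes 13.5 (f = 0), 25.8 (0.25), 33.9 (0.5) or 42.4 (1). At 16 v 16 weeks it stays between 13.5 and 15.0.

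**What a person-time rate does.** Expected time to first event or end of follow-up is 0.20/h + 0.80(T − 12) when f = 0 and p = 20%. This is 10.76 + 19.2 = 29.96 weeks at T = 36, and 10.76 + 3.2 = 13.96 weeks at T = 16. The rates are 20/29.96 = 0.67 and 20/13.96 = 1.43 subjects per 100 subject-weeks, although the true risks are identical. With front-loaded events the rate therefore errs in the opposite direction.

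**The case against.** The case for leaving the plan alone is substantial.

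1. **The equal-follow-up comparison already exists.** It is prespecified in Protocol 9.4.2 and SAP 8.1, and covers all AEs, related AEs, severity, serious AEs and special-interest AEs. This stands.
2. **Interim-only marking does not lose it.** A reader might infer that the comparison disappears at the final analysis. SAP 3.1 holds the interim until every subject has completed phase 1 or week 24, or has withdrawn. Every 84-day window has then closed, so a re-run would repeat the result apart from data corrections. The primary MMRM table (2.4) is marked in the same way. This stands; the gap is in presentation, not in data.
3. **Not all disclosure is affected.** Tables 3.2-3.4, 3.6-3.8 and 3.53 are tagged GSK CTR, which the SAP's abbreviation list gives as clinical trial register. This stands; the gap is confined to 3.17, 3.56, 3.69 and 3.74.
4. **Later events may be few.** Protocol 4.6.1 places the rise in residual urine mainly in the first 12 weeks and names cystoscopy and urodynamics among UTI factors. Against that, the same section names routine catheterization. Protocol 5.1 asks patients already on intermittent catheterization to continue it at least 3 times daily throughout the study, and SAP 8.5.2 counts fewer than 5 subjects who void spontaneously without it. A zero late hazard for UTI is therefore unlikely, but its size is unknown.
5. **The imbalance is visible.** Table 1.17 reports double-blind follow-up by arm at interim and final, and no formal hypothesis is tested. That discloses the problem without correcting the AE contrast.

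**Conclusion.** The point holds as a matter of labelling and completeness. Crude full-TC1 results by arm are not directly comparable, because follow-up depends on outcome and nothing adjusts for it. The equal-follow-up window is neither named as the between-arm comparison nor set beside the final, FDAAA/EudraCT and plain-language tables.

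The inflation rests on two conditions: placebo subjects are re-treated earlier, and events keep starting after week 12. The first is likely if the drug works, but the documents give no re-treatment times by arm. Under equal hazards and a 12-week risk of 20%, the artefact is 0 if either condition fails and 7 to 23 points at 36 v 16 weeks for f between 0.25 and 1. Full-TC1 tables at the interim are limited by the week-24 cut, where the 24 v 12 range of 4 to 16 points is the relevant guide. The actual size cannot be fixed from the documents.

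A reader might infer that AEs on active are overstated. The documents do not support that: the active percentage is a valid cumulative incidence over a longer period, and only the contrast with placebo can be distorted.

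**What to change.** 1. State in SAP 8.1 that TC1 ≤84 days is the between-arm AE comparison.
2. At final, repeat or cross-refer to Tables 3.1-3.8, 3.53 and 3.54. Add ≤84-day companions to 3.17, 3.56, 3.69 and 3.74. Keep the full-TC1 versions: for placebo subjects GTC1 starts only at the second injection, so replacing them would drop placebo events between day 85 and that injection from the FDAAA/EudraCT tables.
3. In the full-TC1 tables, add subjects with an event per subject-time to first event. Use AE onset time for subjects with the event, and the TC1 duration already derived in SAP 11.6.2 for the rest. Note that such rates assume a roughly constant hazard and can dilute front-loaded events in the arm followed longer. They supplement the ≤84-day comparison and do not replace it.
4. Footnote follow-up by arm (Table 1.17) on the full-TC1 tables, and state that their crude percentages are not directly comparable between arms.

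The cost is SAP wording and a few more tables or columns. No new data are needed.

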8.2. Adverse Events of Special Interest Analyses

The definition of AEs of special interest and their MedDRA preferred term is described as 11.6.4. The number and percentage of subjects experiencing an AE of special interest and the total number of AEs of special interest will be summarized. Listing will also be produced.

8.3. Clinical Laboratory Analyses

Laboratory evaluations including the analyses of Chemistry laboratory tests, Hematology laboratory tests, Urinalysis, and liver function tests will be based on GSK Core Data Standards. The details of the planned displays are in [Appendix 10: List of Data Displays](#).

Clinical laboratory analyses will be by treatment group (and total for GTC1, GTC2, GTC3) and study phases (i.e., TC1, GTC1, GTC2 and GTC3, see section 11.4. Note that TC1 <= 84 days and Overall will not be included for these analyses).

Raw value and change from baseline for laboratory data will be summarized by treatment group (and total for GTC1, GTC2 and GTC3) for each visit.

Shifts from baseline relative to the normal range will be also summarized by treatment group (and total for GTC1, GTC2 and GTC3) for each visit.

Worst case urinalysis results relative to baseline for protein (category: NEG, TRA, 1+, 2+, 3+, 4+) and occult blood (category: NEG, TRA, 1+, 2+, 3+) urinalysis only will be summarized by treatment group (and total for GTC1, GTC2 and GTC3) for each study phases (TC1 and GTC1, GTC2 and GTC3). The categories for worst case are: No Change/Decreased, Any Increase, Increase to TRA, Increase to 1+, Increase to 2+, Increase to 3+, Increase to 4+. The categorization is determined by comparing the baseline category to the worst case post-baseline category. The determination of the worst case post-baseline takes into account both planned and unscheduled assessments. The percentages are based on the number of subjects in the treatment group with data for the test post-baseline. Subjects with missing baseline value are to be assumed to have normal/within range baseline value.

For Chemistry and Hematology data, the scatter plots between baseline and Week12/Withdrawal will be prepared by treatment group for TC1.

In order to provide detailed information regarding liver monitoring/stopping events which are classified as adverse events in case that these events occurred, following summary and listings (IDSL number to use) will be provided.

- Summary of Hepatobiliary Laboratory Abnormalities(LIVER10)
- Listing of Medical Conditions for Subjects with Liver Stopping Events (MH2)
- Listing of Substance Use for Subjects with Liver Stopping Events (SU2)
- Listing of Liver Monitoring/Stopping Event Reporting(LIVER5)
- Listing of Liver Stopping Event Information for RUCAM Score(LIVER6)
- Listing of Liver Biopsy Details(LIVER7)
- Listing of Liver Imaging Details(LIVER8)

- Listing of Subjects Meeting Hepatobiliary Laboratory Criteria Post-Baseline(LIVER13)

